TPE intervention	
 • Non-index case, and • Resided or spent at least one night in the Target Area in the past 5 weeks. 	
 • Target Area overlaps with prior Target Area that received the TPE intervention within the past 8 weeks, and • For DP specifically (though still eligible for interview): 
 — Temperature $\geq 38.0^{\circ}\text{C}$, report of fever in the past 48 hours, or other illness (will be referred to the nearest health facility for further evaluation) — Pregnancy, breastfeeding, and women who have had menarche but no menses in the past 4 weeks — Children <9 months of age or <7 kg — Known allergy or history of adverse reaction to DP — Already taken 2 courses of DP in the past year or taken 1 course within the past 2 months — Moderate or severe renal or hepatic insufficiency — Currently with severe malaria — Family history of sudden death or of congenital prolongation of the QTc interval. — Known congenital prolongation of the QTc-interval or any clinical condition known to prolong the QTc interval. — History of symptomatic cardiac arrhythmias or with clinically relevant bradycardia. Any predisposing cardiac conditions for arrhythmia such as severe hypertension, left ventricular hypertrophy (including hypertrophic cardiomyopathy) or congestive cardiac failure accompanied by reduced left ventricle ejection fraction. — Electrolyte disturbances, particularly hypokalaemia, hypocalcaemia or hypomagnesaemia (including vomiting in child) — Recent treatment with medicinal products known to prolong the QTc interval that may still be circulating at the time that DP is commenced (e.g. mefloquine, halofantrine, lumefantrine, chloroquine, quinine and other antimalarial agents)
Pill count	
 • Resides in the first Target Area to receive the intervention for each locality during each transmission season, and • Received antimalarial drugs through the TPE intervention. 	
 • Resides in a locality randomized to the RACD arm.
Acceptability Assessment	
 • Received the TPE intervention, or • Member of surveillance team in both RACD and TPE arms. 	
 • < 18 years of age.

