If an individual cannot safely be given DP, that individual will not be given medication for presumptive treatment. Pregnant women and breastfeeding women will be excluded. All girls ≥ 10 years of age will also be asked about menses. Those who have had menarche but have not menstruated in the past 4 weeks will also be excluded. Infants < 9 months of age or < 7 kg will also be excluded. For infants and children unable to take tablets, drugs will be crushed, mixed with water and administered as a suspension. No more than two courses of DP may be given within a 12-month period. Additionally, a second course of DP should not be given within 2 months after the first course due to the long elimination half-life of piperazine. Other contraindications include: severe malaria, young children who vomit (electrolyte disturbances can increase QTc), heart problems or rhythm disturbances, kidney or hepatic insufficiency, recent treatment with certain medications (antiarrhythmics, neuroleptics, antibiotics, non-sedating antihistamines, antimalarial agents, and others (cisapride, droperidol, domperidone, bepridil, dephemanil, probucol, levomethadyl, methadone, vinca alkaloids, and arsenic trioxide).

Individuals who cannot safely be given DP will be tested by RDT using the *Pf*-specific First Response RDT during the intervention visit. At the time that blood is collected for RDT testing, the same finger prick will be used to generate a slide and dried blood spot. Four spots of blood will be collected for each DBS. A second finger prick will be used to collect microtainer blood samples from RDT-positive individuals. Subjects testing positive by RDT will be referred to the closest health facility for treatment with a drug that is safe for them according to national policy.

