14.2 Outcome measures

Table 6. Outcome measures

Outcome	Indicator
Primary Aim	
Incidence	Cumulative incidence of all cases (Pf infection) identified by passive surveillance in the locality subsequent to the first reported case during the study period (not including additional cases found through RACD). Cases include both locally acquired and imported infections.
Secondary aims (effectiveness)	
Exposure (seroprevalence)	Seroprevalence to markers of recent exposure using ELISA in end-line survey samples taken from residents in Target Areas near the end of the study (expected mid 2017), excluding index cases detected through passive surveillance.
Infection prevalence	Prevalence of infection by LAMP and QTNASBA testing for gametocytes in LAMP positives in end-line survey samples taken from residents in Target Areas near the end of the study (expected mid 2017), including index cases detected through passive surveillance.
Time to first local post-intervention incident case	Time to first incident local case in the Target Area subsequent to the intervention. Target Areas that receive a repeat intervention will qualify to be included again at subsequent interventions.
Proportion of imported incident cases	Proportion of imported incident cases in the locality subsequent to the first reported case will be measured through passive surveillance. Additional cases found through RACD will not be included.
Transmission potential (by genotyping)	Microsatellite genotyping will be performed on samples collected from index cases as well as secondary cases.
Secondary aims (feasibility)	
Coverage	Proportion of persons residing within approximately 200m (TPE localities) or 500m (RACD localities) of the index case who consented to participate in the study and who completed the initial procedures for their study arm (finger prick for RDT in the RACD arm, initial dose of DP in the TPE arm)
Adherence	Proportion of persons who completed 3 days of therapy among all individuals initiated on DP in the TPE arm, as assessed by pill count
Prevalence of SAEs related to treatment	Proportion of subjects experiencing SAEs deemed possibly, probably, or definitely related to DP or AL, out of the total number of subjects enrolled
Acceptability	Qualitative assessment (See Section 10)
Cost	Cost per index case-level intervention, cost per case averted.

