Cement block or brick

Plaster

No observation conducted

42. *Observe:* What is the roof primarily comprised of?

Grass or palm

Metal sheets or tile

No observation conducted

43. *Observe:* Does the structure where the person sleeps have windows? Yes No

If yes, observe: Are the windows screened or covered? Yes No

44. *Observe:* Are there cracks/spaces at the eaves of the structure? Yes No

45. *Ask:* Has this home be sprayed in the past year? Yes No Don't Know

If yes, ask to see spray card to confirm house has been sprayed.

Spray card confirmed

No spray card

Cannot find spray card

If yes, were all the houses sprayed? Yes No Don't Know

If yes, do you sleep under a sprayed structure? Yes No Don't Know

46. *Ask:* Does your household own a bed net? Yes No

If yes, ask: How many bed nets do you have in the household? _____

How many are treated with insecticide? _____

Did you sleep under your bed net anytime within the past week? Yes No

If yes, ask: Is your bed net treated with insecticide? Yes No Don't Know

If no, ask: Why didn't you sleep under a bed net within the past week?

Too hot

- Too cold
- Used by someone else
- Net not hung up
- Net worn out/poor condition
- Net dirt
- Net bad for health
- Don't like shape or color
- Other _____

47. Are there any water bodies around or near the house? Yes No Don't Know

If yes, ask: what kind of body of water (check all that apply):

- river lake reservoir pond other, specify: _____

If yes, ask: What is the closest distance to a water body?

- <50m 50-99m 100-499m 500m-999m ≥1 km

Thank you for our participation in this study.

48. As mentioned, we would like to return in 6-9 months to check on the resolution of your infection. We would also like to return in mid 2017 to check on whether there continues to be malaria in your community; at this visit we would like to collection in your family and neighbours in addition to you. Each visit will only take a few minutes. Your participation in these follow-up studies will be voluntary. Are you willing to be contacted for these follow-up visits?

- Yes No Don't Know

49. Case Investigation Comments: Is there any other information that is relevant for this case investigation?

Case Determination *(To be conducted by supervisors following completion of investigation)*

50. *Origin of infection*

- Local
- Imported from another country
- Imported from another area of Swaziland
- Unknown
- Other

51. *Case epidemiology*

- Index
- Secondary case from RACD

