- Secondary case but identified in health facility
- Unknown
- Other

Response Determination *(To be conducted by supervisors following completion of investigation)*

52. *Please check all that apply regarding the response:*

- Receptive area –TPE study locality

- TPE planned
- TPE not planned as already completed in the past 8 weeks, note aciid: _____ and patient name _____

- Receptive area: RACD study locality
 - RACD planned
 - RACD not planned as already completed in the past 5 weeks, note aciid: _____ and patient name _____

- Receptive area: Non-Study locality
 - RACD planned
 - RACD not planned as already completed in the past 5 weeks, note aciid: _____ and patient name _____
 - Imported Network screening planned
 - Other, explain _____

- Non -receptive area
 - Imported Network screening planned
 - RACD planned, explain why _____
 - Other, explain _____

53. Response comments

54. Determination conducted by _____

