- *If yes, ask: Where did you sleep overnight, when did you sleep there, why did you sleep there, and personal protection? If slept outside Swaziland, also ask about means of travel and border post of re-entry.*

Within Swaziland				
Town / Locality / Inkhundla	Duration of Stay		Reason for sleeping away from current residence: -previous residence -business -holiday -visiting friends/family -other (specify, ____)	Personal protection -chemoprophylaxis (specify__) -bednet -mosquito repellent or coil -None
	First Night YY/MM/DD	Last Night YY/MM/DD		
a.				
b.				
c.				
d.				
e.				

Outside of Swaziland							
Country	Province / Town	Duration of Stay		Reason for sleeping away from current residence: -previous residence -business -holiday -visiting friends / family -other (specify____)	Personal protection -chemoprophylaxis (specify__) -bednet -mosquito repellent or coil -None	Means of travel -Large bus -Kombi (van) -Personal car -Ride share (catch a ride / got a lift) -Airplane -Bicycle -Walked -Other (specify____)	Border Post of Re-Entry - Lavumisa/Golela - Salitje/Onverwacht - Mahamba - Gege/Bothashoop - Sicunusa/Houtkop - Sandlane/Nerston - Ngwenya/Oshoek - Bulembu/Josefsdal - Matsamo/Jeppe's Reef - Mananga - Lomahasha/Namaacha - Mhlumeni/Goba - KMIII International Airport - Other
		First Night YY/MM/DD	Last Night YY/MM/DD				
a.							
b.							
c.							
d.							
e.							

10. *Comments or any other information that is relevant?*

11. RDT result: positive negative not done

If positive, patient referred to local health facility Yes No

If no, why? _____

DBS collected Yes No Not Done

If DBS not done, why? Patient refused Other _____

Thank you for our participation in this study.

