19. In the past month have you taken antimalarial drugs for either treatment or prevention of malaria (mefloquine, halofantrine, lumefantrine, chloroquine, or quinine)? Yes No Don't know

20. Have you had a fever in the past 48 hours, or are otherwise feeling ill? Yes No Don't know

If Yes, was subject taken to local health facility? Yes No

21. Are you currently taking any medications? Yes No Don't know

If Yes, are you taking any of the following medications? (check all that apply)

a. Medicines that effect heart rhythms (such as amiodarone, disopyramide, dofetilide, ibutilide, procainamide, quinidine, hydroquinidine, or sotalol)

b. Medicines that treat depression

c. Medicines that treat mental health problems (such as phenothiazines, sertindole, sultopride, chlorpromazine, haloperidol, mesoridazine, pimozone, or thioridazine)

d. Medicines that treat infection (macrolides [such as erythromycin or clarithromycin], fluoroquinolones [such as moxifloxacin or sparfloxacin], medicines for fungal infections [such as imidazole and fluconazole], as well as pentamidine [used to treat a specific type of pneumonia] and saquinavir [for treatment of HIV])

e. Antihistamines used to treat allergies or inflammation (such as terfenadine, astemizole, mizolastine)

f. Medicines that treat stomach problems such as cisapride, droperidol, domperidone, or diphemanil

g. Medicines to treat cancers (vinca alkaloids, arsenic trioxide), chest pain (bepridil), drug addiction (levomethadyl, methadone), and high cholesterol levels (probucole)

Drug Administration: (Subject is eligible to receive medication if they weigh at least 7kg and answered "No" to questions 10-19 and are not taking any of the medications listed in 20a-20g)

22. Is the subject eligible to receive medication? Yes No

Tablet to automatically say Yes or No for eligibility of individual to receive medication based on responses above and criteria provided, options should be greyed out (disabled).

a. *If yes, indicate regimen administered:*

Check one	Weight band	Color of box	Regimen administered	Subscription
	7-12 kg	Bottle	320 mg piperazine /40 mg dihydroartemisinin tablets, 3 half tablets	½ tablet daily x 3 days
	7-12 kg	Pink box	160 mg piperazine /20 mg dihydroartemisinin tablets, 3 tablets	1 tablet daily x 3 days
	13-23 kg	Green box	320 mg piperazine /40 mg dihydroartemisinin tablets, 3 tablets	1 tablet daily x 3 days

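### Case ascertainment for the primary outcome differs by arm: infections met at the intervention visit are named, recorded and excluded in RACD, while in TPE they are not reliably recorded and the status of ill residents referred untested is undefined

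*Combined protocol and SAP*

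**What the plan says.** Table 6 defines the primary outcome as the cumulative incidence of cases "identified by passive surveillance in the locality subsequent to the first reported case during the study period (not including additional cases found through RACD"). Its only named exclusion is the phrase "not including additional cases found through RACD". The row on the proportion of imported cases repeats the RACD exclusion. The row on time to first local case has no exclusion.

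In RACD, everyone in the Target Area is tested by RDT (section 7.2). The individual form records the result (Appendix I question 11: "RDT result: positive negative not done"), and item 51 of the case investigation form (Appendix C) offers "Secondary case from RACD".

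In TPE, Table 3 lists fever or other illness as a reason not to give DP and says that such people "will be referred to the nearest health facility for further evaluation"; section 7.4 says much the same without naming an arm. Section 7.3 adds: "Individuals who cannot safely be given DP will be tested by RDT", with referral if positive, and Table 4 agrees. Section 4.1 says that no blood is collected in TPE. Appendix K question 20 asks, of ill people, "If Yes, was subject taken to local health facility", but records no test result. Item 51 of Appendix C has no TPE counterpart to the RACD category. Its nearest specific option is "Secondary case but identified in health facility", and no rule says whether cases so coded count.

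**The concern.** The visit follows an index case, so any infection met there falls after the locality's first case and inside the counting period. The same clinical picture, an ill and infected neighbour on the visit day, can be handled differently by arm. In RACD the person is tested, recorded and excluded by name. In TPE the person may be referred without a test, diagnosed at a facility and notified through the hotline, and then looks like any other passive case.

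At stake is whether the numerator means the same thing in both arms. The trial is open-label and the outcome is rare. Without a prespecified rule, these cases would be classified afterwards with the arm known, and RDT results that were never entered may not be recoverable.

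**Working it through.** **Step 1. Follow one ill, infected resident through each arm.**

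| Step | RACD | TPE |
|---|---|---|
| Test at visit | RDT for all (7.2) | RDT (7.3, Table 4); referral only (Table 3, 7.4); no blood collected (4.1) |
| Result on individual form | Appendix I question 11 | No field in Appendix K |
| Positives on dashboard | Counted (Appendix H) | Not counted (Appendix J) |
| Case category, Appendix C item 51 | RACD secondary case | No TPE option |
| Table 6 | Excluded by name | Team-tested: outside passive surveillance, but not traceable. Referred untested: not addressed |

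Section 7.1 fits this pattern: the RACD questionnaire is to collect blood results, the TPE questionnaire doses.

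**Step 2. Inputs for the size.** The documents give no figure for infections found at TPE visits.

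- RDT positivity at past RACD visits (section 1.3): 42/8355 = 0.503%.
- TPE persons (section 14.3): 66 index cases and 1782 people treated. This reproduces as 66 × 30 × 0.9 = 1782, with 30 people per index case and 10% repeat encounters from section 14.1.
- Planned ratio (section 14.3): 0.2% / 0.4% = 0.50.
- Share f of positives who are ill or cannot take DP and end up counted: not in the documents. I assume 10–25%.
- Expected TPE cases B, three readings: 66 index cases; 0.2% × 55,928/2 = 55.9; 0.2% × 41,328/2 = 41.3.

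**Step 3. Extra cases.** E = 1782 × (42/8355) × f = 8.96 × f. For f = 10%, E = 0.90; for f = 25%, E = 2.24.

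**Step 4. Apparent ratio**, holding the RACD count fixed: R = 0.50 × (1 + E/B).

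| B | f = 10% | f = 25% | f = 100% |
|---|---|---|---|
| 66 | 0.507 | 0.517 | 0.568 |
| 55.9 | 0.508 | 0.520 | 0.580 |
| 41.3 | 0.511 | 0.527 | 0.608 |

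**Step 5. Other inputs.** With 66 × 30 = 1980 people, the 10–25% range becomes 0.508–0.530. An outer bound takes all 53 residents within 200 m (section 4.4) and counts every positive: 66 × 53 × 0.503% = 17.6 extra cases, a ratio of 0.63–0.71. That would need every positive to be ill or ineligible and none to be excluded, which is not realistic. In the other direction, 0.5% comes from everyone screened and may understate positivity among ill people.

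**The case against.** **Both arms are already limited to passive cases.** Table 6 starts from passive surveillance, and the index-case row of Table 3 bars infections found by screening as triggers in either arm. The RACD parenthesis can be read as a clarification for the arm with mass testing. This stands for TPE residents tested by the team: they are arguably excluded already, so it would be wrong to say that TPE has no exclusion at all. But the exclusion cannot be applied reliably when the form holds no result, and it does not settle the case of someone referred untested.

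**Referral happens in both arms.** Section 7.4 is not limited to TPE, and RACD positives also go to a facility. That stands. No section says how a facility diagnosis after team referral is counted in either arm. The difference is that RACD residents carry a recorded test from the visit.

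**The direction is unknown.** A reader might infer that the comparison is biased against TPE. The documents do not support that as a conclusion. Sections 4.4 and 7.2 turn RACD secondary cases into index cases, against Table 3, and that route could add cases to RACD. The 6–9 month visit tests non-index residents from RACD localities only. Most infections present at a TPE visit would be treated without a test and never diagnosed. RDT sensitivity in RACD is put at 20% against PCR, so most infections there are missed and could present later as counted cases.

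**The forms may have a workaround.** Appendix D lists active case detection as a source, and Appendix C item 51 has a catch-all option. The options of Appendix C item 10 are not readable in the text available, so I draw nothing from them. A code would help with tracing, but it is not a counting rule.

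**Conclusion.** The point holds as a gap in definition and recording that makes ascertainment of the primary outcome depend on arm. The RACD-only wording of Table 6 and of Appendix C item 51, the missing RDT field in Appendix K, and the undefined status of residents referred by the team can all be checked in the text. That untested referrals in TPE would in fact be counted is an inference; the documents leave it open.

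The likely size is about 1–2 extra TPE cases and a ratio of 0.51–0.53 in place of 0.50. This rests on the assumed 10–25% share, on 0.5% positivity and on no offset in RACD. It would not overturn a clear result. It is worth correcting because the correction is cheap and the missing results may be unrecoverable later.

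**What to change.** 1. Replace the Table 6 clause with one rule for both arms: exclude from the primary numerator any infection diagnosed at a study visit (intervention, 6–9 month or end-line), or at a facility on referral from one. State the window in days in advance. Apply the same rule to the imported-proportion and time-to-first-case outcomes.
2. Match on the case investigation record, since the facility notification form (Appendix B) shows no study barcode.
3. Add an RDT result and a referral outcome to Appendix K, and an option for cases detected at or referred from a study visit to Appendix C item 51.
4. Add a sensitivity analysis that counts these cases in both arms, and report the number added per arm. RACD tests everyone, so it will tend to gain more.
5. Reconcile section 4.1, Table 3 and section 7.4 with section 7.3 and Table 4 on testing of ill or DP-ineligible TPE residents, and sections 4.4 and 7.2 with Table 3 on index-case status. Which clinical procedure applies is for the study team to decide.

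The cost is a few fewer primary cases, two form fields, one answer option and some linkage work. The counting rule itself needs no additional visits or tests.

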A Ugandan study of regimens available for intermittent preventative therapy (IPT) - an MDA strategy used in high transmission settings - identified DP as the most effective and best-tolerated regimen among school children [11]. Studies of DP in Uganda, including trials of very young children,[12, 13] children under ten,[14, 15] and school-aged children,[11] have found no increase in safety risk associated with DP consistent with other studies. Additional benefits of DP are that it can be administered just once daily and the long half-life of the partner drug piperazine provides a protection against subsequent infection. Given these characteristics, DP has been suggested as an optimal candidate for community based MDA.[16]

ACTs treat early gametocytes, the parasite stage responsible for subsequent transmission, but they do not treat mature gametocytes. The use of single dose primaquine in addition to ACT has been proposed as a strategy to help interrupt malaria transmission and it is currently recommended by WHO for symptomatic cases. However, there are no guidelines for use in asymptomatics. The potential risk is hemolysis in individuals with underlying G6PD-deficiency. The unavailability of a simple and inexpensive rapid test for G6PD deficiency complicates the use of primaquine. Recent modeling suggests limited added benefit of primaquine to ACT alone in MDA. In an individual with asymptomatic parasitemia, ACT alone is likely to decrease the period of gametocytemia from months to about 2-6 weeks. The addition of primaquine will decrease that period to about one week. The slightly prolonged period of gametocytemia may not be relevant in a low transmission setting, particularly considering the potential risks.

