The sample size for the Target Area assessments is estimated from incidence in the previous transmission season, and the expected drop in incidence among those in the TPE arm; resulting in an estimated 200 index cases total with 30 individuals screened or treated in the Target Areas around each case. With 200 index cases, we expect about 6000 encounters where individuals will receive a study intervention (either TPE or RACD). Based on preliminary RACD data, we anticipate 10% of these encounters will occur in individuals who previously received an intervention during the study period (repeated or overlapping Target Areas). For the follow-up end-line seroprevalence survey, these individuals will only be sampled once. Thus the effective sample size for the seroprevalence outcome measured in the Target Area population is expected to be 5400. Of note, the first index case for each Target Area will not be included since this person's malaria exposure occurred pre-intervention.

For the follow-up end-line infection prevalence survey, index cases will also be included as they will also be at risk for subsequent infection. Thus the effective sample size for the infection prevalence outcome measured in the Target Area population will be 5400 individuals screened plus 200 index cases, or 5600 individuals.

Adherence evaluation:

Adherence will be measured on a subsample that includes only the individuals in the Target Areas surrounding the first index case in each locality. We expect that 22 localities in the TPE arm will have at least one index case, and at least 30 individuals will be assessed for DP treatment per Target Area, for a total sample of 660 individuals.

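### End-line infection prevalence counts index cases however recently they were diagnosed, so residual positivity from the triggering infection can be scored as an end-line infection

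*Combined protocol and SAP*

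**What the plan says.** Table 6 in section 14.2 gives the outcome as "Prevalence of infection by LAMP and QTNASBA testing for gametocytes in LAMP positives", measured in Target Area residents at the end-line survey, "including index cases detected through passive surveillance". Section 14.1 gives the reason: "index cases will also be included as they will also be at risk for subsequent infection". Table 3 lists no exclusion criterion for the end-line survey. No section sets an interval since diagnosis or says how a residual positive is to be classified.

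Section 14.1 treats seroprevalence differently: "the first index case for each Target Area will not be included since this person's malaria exposure occurred pre-intervention". Section 14.3 repeats that rule, whereas Table 6 leaves all passively detected index cases out of seroprevalence.

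On persistence, section 1.6 says of asymptomatic parasitaemia that "ACT alone is likely to decrease the period of gametocytemia from months to about 2-6 weeks", and that adding primaquine shortens this to about one week. Section 2 places the survey at the end of the transmission season. Appendix O asks about malaria diagnoses since the intervention, antimalarial use in the past 2 months and the start date of the last treatment, but the outcome definition uses none of these answers.

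**The concern.** The reason given for including index cases concerns new infections. The rule as written also counts what is left of the old one. Take an index case diagnosed on 10 May 2017, treated, and sampled on 31 May. If that sample is LAMP-positive from residual gametocytes, the rule records one end-line infection, although no subsequent infection has occurred.

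Neither intervention could have prevented such a positive where the index case triggered the area's first intervention. Section 2 already warns that post-intervention prevalence may be too low to compare the arms, so even a few such positives could affect a ratio measure.

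**Working it through.** **The plan's own sample size.** Section 14.1 has the sample "resulting in an estimated 200 index cases total with 30 individuals screened or treated" around each case, and "we anticipate 10% of these encounters will occur in individuals who previously received an intervention during the study period".

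- 200 × 30 = 6,000 encounters; 6,000 × 0.90 = 5,400 people; 5,400 + 200 = 5,600. This reproduces "5400 individuals screened plus 200 index cases, or 5600 individuals".

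**By arm.** Section 14.3 (Coverage) expects 66 TPE index cases, which leaves 200 − 66 = 134 in RACD.

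- TPE: 66 × 30 × 0.9 = 1,782 residents (the figure in 14.3), plus 66 = 1,848.
- RACD: 134 × 30 × 0.9 = 3,618 residents, plus 134 = 3,752.
- Index-case share: 66/1,848 = 134/3,752 = 3.6% in each arm.

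**Recent index cases.** September 2015 to mid-2017 is taken as 22 months, or 22 × 52/12 = 95.3 weeks. With even reporting, the number diagnosed within w weeks of the survey is 200 × w/95.3:

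- w = 2: 4.2 (TPE 1.4, RACD 2.8)
- w = 6: 12.6 (TPE 4.2, RACD 8.4)

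**Carry-over.** Let q be the share still LAMP-positive. The documents give no value, so q is varied from 10% to 50%.

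- Low: 4.2 × 0.10 = 0.42 positives
- High: 12.6 × 0.50 = 6.3 positives

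**Effect on the contrast.** Take the 35 survey infections expected in section 14.4 as true infections, with a true TPE/RACD ratio of 0.25 (illustrative).

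- RACD prevalence = 35/(3,752 + 1,848/4) = 0.83%, or 31.2 infections.
- TPE prevalence = 0.83%/4 = 0.21%, or 3.8 infections.
- True difference = 0.62 percentage points.

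Adding the carry-over positives to each arm gives:

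| Window, q | Extra positives | TPE | RACD | Ratio | Difference (points) |
|---|---|---|---|---|---|
| 2 weeks, 10% | 0.42 | 0.215% | 0.838% | 0.26 | 0.62 |
| 2 weeks, 50% | 2.1 | 0.245% | 0.868% | 0.28 | 0.62 |
| 6 weeks, 10% | 1.26 | 0.230% | 0.853% | 0.27 | 0.62 |
| 6 weeks, 50% | 6.3 | 0.320% | 0.943% | 0.34 | 0.62 |
| 6 weeks, 100% (bound) | 12.6 | 0.432% | 1.055% | 0.41 | 0.62 |

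With a true ratio of 0.50, the same 10% to 50% range gives 0.505 to 0.565. The difference stays constant because index cases are the same share of both arms, so each arm gains the same number of percentage points.

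**Cost of an 8-week exclusion.** 200 × 8/95.3 = 17 people. If all cases fall in two November-June seasons (16 months, about 69 weeks), 200 × 8/69 = 23 people.

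**The case against.** The case for leaving the rule alone has several parts.

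- **Inclusion is deliberate and reasoned.** Most index cases are diagnosed well before the survey, and for them a positive is far more likely to be a new infection. This stands, and it is why all index cases should not be dropped.
- **The seroprevalence parallel is imperfect.** Serology measures exposure, and the first index case's exposure is known to precede the intervention. A treated infection does not remain current indefinitely, so different rules are defensible. The parallel shows only that the plan recognised the issue for one outcome.
- **Persistence is uncertain.** The 2 to 6 weeks refers to gametocytaemia in asymptomatic infection, not LAMP positivity in treated clinical cases. Section 1.6 also says WHO recommends primaquine for symptomatic cases, and the Appendix C form lists it as a possible treatment. At one week, only 200/95 = 2 to 200/69 = 3 index cases would be affected. Section 1.3 suspects that LAMP on dried blood spots misses infections. All of this argues for a low q.
- **Stakes are limited.** Table 9 shows no power calculation for this secondary outcome. Genotyping of survey infections might separate old from new, but the prevalence definition makes no use of it.

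A reader might infer that carry-over could supply up to half of the expected infections (200 × 6/69 = 17.4; 17.4/35 = 50%). That needs every recent case to stay positive and all cases to fall within two seasons, while section 1.1 says recent local cases do not follow a seasonal pattern. A reader might also infer that every index infection precedes the intervention. A later index case in an already treated Target Area does not, and section 14.3 keeps such cases in seroprevalence.

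**Conclusion.** The gap is real: the definition can score the triggering infection as an end-line infection, contrary to the reason given for including index cases. The likely size is modest, about 0.4 to 6.3 positives against 35 expected, which moves a true ratio of 0.25 to about 0.26 to 0.34.

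This rests on even reporting over about 95 weeks, on the 2 to 6 weeks applying to treated index cases, on q between 10% and 50%, and on equal carry-over by arm.

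It would go too far to say that the arm contrast is diluted on every scale. Section 14.4 specifies GEE but no link or effect measure, and the risk difference is essentially unchanged while index-case shares are equal. If the 500 m RACD areas yield more survey participants per index case than the 200 m TPE areas, carry-over would weigh more on TPE and the difference would shift too. If recent index cases split unevenly, the bias could run either way.

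Nor should the rates printed in section 14.4 serve as a benchmark for a four-fold contrast. They put 1.6% in TPE and 0.4% in RACD, against the stated hypothesis. They also give 56 infections if 5,600 people are split equally (2,800 × 0.020), not 35; about 1,782 per arm would give 35.6.

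**What to change.** In Table 6 and section 14.1, pre-specify before the end-line survey an infection-prevalence analysis that removes, from numerator and denominator, passively detected index cases diagnosed or treated within a fixed window before their end-line sample. Eight weeks is one choice: it exceeds the 6 weeks in section 1.6 and matches the 2-month recall in Appendix O. Apply it identically in both arms, report it beside the all-inclusive figure, and state which of the two is the main result. The all-inclusive figure can keep that place.

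Do not extend the exclusion to RDT-positive secondary cases. Residents are tested in RACD (section 7.2), but in TPE only those who cannot be given DP are tested (section 7.3). The exclusion would therefore remove known recent infections mainly from one arm.

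The cost is a sentence in each place and no new data, since case report dates and the Appendix O treatment dates are already collected. About 17 to 23 of 5,600 people leave that analysis, including some index cases whose infection arose after an earlier intervention. Any wording borrowed from the seroprevalence rule needs reconciling first: Table 6 drops all passively detected index cases, while sections 14.1 and 14.3 drop only the first in each Target Area.
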